### 5.2.2 Exclusion Criteria

- No exposure to either oral or iv LCM within the 3 months prior to the index date
  - In the case of patients  $< 90$  days of age, no prior LCM ever in the record

A separate cohort for patients  $< 30$  days old is established with the following criteria.

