### • Study design, including data sources

#### *Study Design*

A retrospective cohort study will be conducted using data from the PEDSnet database to achieve the study objectives. Electronic health record (EHR) data will be collected from January 2009 to December 2018. Two mutually exclusive cohorts will be identified, the first

cohort consisting of pediatric patients treated with higher than the recommended IV LCM doses, and the second (comparator) cohort comprising pediatric patients treated with recommended initial/maintenance IV LCM dose. The index date will be defined as the initiation of a new IV LCM treatment episode/receipt of a higher IV LCM dose than known maintenance dose. The exposure period will be the period between the index date (as defined above) and discontinuation of LCM. Subjects will be followed from the index date up to 30 days after discontinuing treatment with LCM or censoring, and during this time will be assessed for occurrence of described study outcomes. All subjects require a baseline period prior to the index date free of either oral or IV LCM. In the stratified assessment of increasing LCM loading dose, follow up will be from the index date up to 24 hours and 7 days after discontinuing treatment with IV LCM. Outcome ascertainment will be done in two ways, 1) data elements within the PEDSnet common data model (CDM) will be examined to identify select medical events of interest; and 2) a chart review of the EHRs for all eligible study patients will be conducted to examine unstructured, text data not captured in the CDM to identify the select medical events of interest.

Patients with status epilepticus diagnostic codes in their record will be identified from the cohort and will have their results presented separately in sub tables. They will also contribute to the main study populations. This is to fulfill commitment to examine outcomes in SE patients when exposed to lacosamide.

- **Data analysis**

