### 5.2.4 Neonates exclusion criteria

- No exposure to either oral or iv LCM prior to the index date

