### 5.5.4 Exposure Definition and Measurement

The study population for this study is pediatric patients treated with higher IV LCM doses and recommended initial/maintenance IV LCM dose. Lacosamide will be identified based on prescription or dispensing data from the medications table in the PEDSnet CDM using RxNorm codes ([Table 1 RxNorm codes for Lacosamide](#)), and if needed the free text will be reviewed for further details about the LCM dosage. The equivalent NDC codes have been provided in [Table 2 NDC codes for Lacosamide](#).

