**Table 1 RxNorm codes for Lacosamide**

RxNorm CUI	Term	Term Type
1734186	lacosamide injection [Vimpat]	Branded Drug Form
1734189	lacosamide 10 mg/ml injection [Vimpat]	Branded Drug
809984	20 ml lacosamide 10 mg/ml injection [Vimpat]	Quant Branded Drug
809974	20 ml lacosamide 10 mg/ml injection	Quant Clinical Drug

RxNorm CUI	Term	Term Type
1734184	lacosamide injection	Clinical Drug Form
1734188	lacosamide 10 mg/ml injection	Clinical Drug
1186608	Vimpat Injectable Product	Branded Dose Group
1161965	lacosamide Injectable Product	Clinical Dose Group

These subsume exposures that would be described by the following National Drug Codes (NDC) (current and prior) in other data sources as indicated below in [Table 2](#).

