### **5.9.2 Handling of Missing Data**

Data is dependent on information that was recorded by physicians and nurses into the EHR. It is therefore assumed that the patient did not have the diagnosis of interest if it is not reported in the EHR. No missing data will be imputed. For demographic characteristics, the type of missingness will be evaluated.

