### 5.9.4 Strength and Limitations

**Unmeasured confounding:** As the study is comparing the incidence rates of select medical events in patients who are treated with a high dose of IV lacosamide to patients who are treated with recommended dose of IV lacosamide, the major confounders are factors that impact the incidence rate of these medical events of interest. These factors include age, gender, comorbidities, and exposure to other medications which are measured. Unmeasured confounding would only occur if there was a major confounder which is not measured and thus missed from the adjusted model. However, the electronic medical records include demographic information, the medical history of the patients and any medications prescribed by the physicians. Therefore we anticipate that information on most of the confounders will be available. It is possible that there will be missing information on some comorbidities, if they are not recorded by the physicians and on medications that are either bought over counter or prescribed outside the PEDSnet healthcare network. Nevertheless, most hospitals in the PEDSNet healthcare network are large with epilepsy comprehensive care centers within the neurology departments, so we anticipate reliable background medical. We do not anticipate that there will be a disproportionate difference in the recording of the medical history data and prescription of medications in patients who are treated with high dose lacosamide and recommended lacosamide prior to the index date. Therefore, we anticipate that there will be minimal unmeasured confounding. Additionally, the analysis will be using new user design to minimize confounding by indication.

**Reduced generalizability:** The PEDSnet database is restricted to subjects seeking and receiving medical care within a facility affiliated with PEDSnet. Data is obtained from multiple care sites and type (e.g. in-patient, out-patient, emergency department). However, if a report of an event was made or a subject was treated for an event at a facility that is not affiliated PEDSnet, this information will not be captured in the PEDSnet data. However, as most events are anticipated to occur within 24 hours of receiving IV LCM, the impact of this is likely to be low.

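### The LCM-free criterion is worded in reverse and not enforceable as specified: no oral codes, no test of baseline observation, and a conflicting index route, so the new-user claim is not secured

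*Protocol*

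**What the plan says.** Eligibility. Section 5.2.2 of the Protocol, headed Exclusion Criteria, lists "No exposure to either oral or iv LCM within the 3 months prior to the index date", with a sub-item for children under 90 days: "no prior LCM ever in the record". Section 5.2.4, the neonates' exclusion list, has "No exposure to either oral or iv LCM prior to the index date". The Study Design part of the Executive Summary states the aim: "All subjects require a baseline period prior to the index date free of either oral or IV LCM".

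Identification of the drug. Section 5.5.4 says "Lacosamide will be identified based on prescription or dispensing data from the medications table in the PEDSnet CDM using RxNorm codes", pointing to Table 1, with equivalent NDC codes in Table 2. A typical Table 1 entry is "lacosamide Injectable Product".

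Baseline and index date. Section 5.2.1 takes the earliest IV administration as the index and asks for no earlier encounter. Section 5.3.1 says that both cohorts need a 3-month baseline. For the higher-dose cohort it offers two index routes: a new IV treatment episode, or a first IV dose above the child's established maintenance dose. The Executive Summary and 5.1 repeat the second route.

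Reliance on the result. Section 5.9.4 says that "the analysis will be using new user design to minimize confounding by indication". On unrecorded diagnoses, 5.9.2 says: "It is therefore assumed that the patient did not have the diagnosis of interest if it is not reported in the EHR".

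**The concern.** The LCM-free rule decides who is in every analysis, and it is what makes this a new-user comparison. Four things weaken it: its polarity is wrong, the only code lists given miss the oral route, no rule separates a child with no LCM from a child with no record, and one index route assumes that the child is already taking LCM.

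The Protocol says oral LCM is approved in the USA from 4 years of age, so earlier oral use is realistic in much of this population. A child who has already taken and tolerated the drug may have a different event risk from a child who has not. If such children count as new users, the protection claimed in 5.9.4 is weaker than stated. A child without earlier network records can also enter the propensity model of 5.9.1.1 with no comorbidity and no earlier antiepileptic drug, because nothing was recorded.

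**Working it through.** The Protocol gives no figure on this point, so there is none to reproduce. The check compares sections, counts codes and adds two illustrations on assumed inputs.

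**1. Polarity.** An exclusion criterion removes whoever meets it. A child with no LCM in the previous 3 months meets the item in 5.2.2 and is removed; a child with recent LCM stays. The Executive Summary asks for the opposite. The under-90-days item and 5.2.4 have the same reversal. It is operative text: the amendment section repeats it as the current wording.

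**2. Codes.** Table 1 has 8 RxNorm entries, 8 of them injectable. Table 2 has 4 NDC entries, 4 of them injectable. Tablet, oral-solution and ingredient codes: 0. The NDC list is described as subsumed by the RxNorm list, so this is one gap and not two. If the index is the earliest IV administration (5.2.1), earlier recorded IV use is nil by construction, and oral use is all that the rule can remove. If the index is a new episode after a clear baseline (5.3.1), earlier IV use is possible too. On either reading the criterion names oral use and no listed code finds it. The rule in 5.3.3 for children who move to oral LCM needs the same codes.

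**3. Observation.** Sections 5.2.1 to 5.2.4 require no encounter before the index. Section 5.3.1 requires a baseline but gives no test that the child was under observation in it. A child whose first network record is the index admission therefore passes. Section 5.9.4 concedes that prescriptions from outside the network may be missing. Chart review is not a secure backstop: 5.1 speaks of all eligible patients, 5.4.1 of roughly 10%. The only baseline sensitivity analysis in 5.9.1.4 shortens the window, to 6 weeks.

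**4. Index route.** A dose above an established maintenance dose presupposes current LCM. Such a child cannot also be LCM-free for the preceding 3 months.

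**5. How many prior users could remain (illustration).** Take the feasibility count of 875 in 5.9.3, which precedes the full criteria. Let p be the share with LCM in the previous 3 months and d the share of these that is detected; both are assumed.

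Retained = 875 × p × (1 − d). Share of kept cohort = retained / [875 × (1 − p) + retained].

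| d | p = 10% | p = 20% | p = 40% |
|---|---|---|---|
| 0 (oral LCM not searched) | 87.5 (10.0%) | 175 (20.0%) | 350 (40.0%) |
| 0.80 | 17.5 (2.2%) | 35 (4.8%) | 70 (11.8%) |
| 0.95 | 4.4 (0.6%) | 8.8 (1.2%) | 17.5 (3.2%) |

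**6. Direction (illustration).** Let s1 and s0 be the shares of prior users in the higher-dose and comparator cohorts, and r their event rate relative to LCM-free children. With a true incidence rate ratio (IRR) of 1.00, the observed IRR = [(1 − s1) + s1·r] / [(1 − s0) + s0·r]. All inputs are assumed; take r = 0.5.

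- s1 = 0, s0 = 0.2: 1 / 0.9 = 1.11.
- s1 = 0.2, s0 = 0: 0.9 / 1 = 0.90.
- s1 = s0 = 0.2: 0.9 / 0.9 = 1.00.

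The sign depends on which cohort holds the prior users, and the Protocol does not say.

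**The case against.** The strongest reply is that these are gaps in specification, not a failed washout.

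- **Codes.** Section 5.3.1 shows that the tables exist to define IV exposure, and an injectable-only list is right for that. Oral LCM can be found in the source: Table 4 says ordered medications are mapped to RxNorm, 5.3.2 evaluates earlier antiepileptic drugs from all available data, and Appendix 14.1 names lacosamide. This stands. A reader might infer that the rule could never be enforced; the documents do not support that. What remains is that 5.5.4 ties identification of lacosamide as such to these tables, and no oral list appears elsewhere in the Protocol. A statistical analysis plan, if one exists, might supply it, but the tables that the Protocol itself fixes leave out a route that its own criterion names.
- **Baseline.** A 3-month baseline is called required, so it is too strong to say that nothing is asked for before the index. That also stands. The missing piece is what counts as having been observed. The assumption in 5.9.2 concerns diagnoses, so it bears on the covariates and not directly on the washout.
- **Wording.** The intent is clear from the Executive Summary, so the reversal is an editorial slip if programmers follow the intent. It does not by itself bring prior users in. It is still the operative wording of an eligibility rule and should not be left to interpretation.
- **Bias.** A reader might infer that prior oral users gather in the comparator and inflate the IRR. The Protocol does not document this. The maintenance-dose route puts current users in the higher-dose cohort, which could push the other way.

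**Conclusion.** The point holds as a defect of specification. The criterion is reversed in 5.2.2 and 5.2.4; the listed codes detect no oral LCM (0 of 8 RxNorm entries, with the 4 NDC equivalents also all injectable); no rule shows that a child was observed in the baseline; and the maintenance-dose index route conflicts with the LCM-free requirement. These four facts come from the text and need no assumption.

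The consequence is a risk: prior LCM users may be misclassified as new users, so the claim in 5.9.4 is not secured. It is not shown that children on oral LCM do enter, or how many. The illustrative shares run from 0.6% to 40% of the kept cohort, depending wholly on assumed prior use and detection. Neither the direction nor the size of any effect on the IRR can be determined from the documents. Because the rule governs every analysis and is cheap to repair, it should be corrected before the cohort is final.

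**What to change.** - **Wording.** Rewrite the items in 5.2.2, including the one for children under 90 days, and in 5.2.4 so that any exposure to oral or IV LCM in the stated window is the ground for exclusion.
- **Codes.** Add ingredient, tablet and oral-solution codes for LCM. State that they serve the washout and the oral-switch rule in 5.3.3, and keep the injectable list for defining IV exposure.
- **Observation.** For children old enough to have a history, prespecify a sensitivity analysis limited to those with at least one network encounter before the index admission. Infants keep the birth-to-index baseline.
- **Index route.** Reconcile the maintenance-dose route in the Executive Summary, 5.1 and 5.3.1 with 5.2.2. Which of them should give way is for the sponsor to decide.

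The cost is a few text edits, a longer code list and one extra run on data already held. Some children may leave the cohort once oral use is searched, and the sensitivity analysis will have fewer patients and wider intervals.

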### 5.2.3 Neonates Inclusion Criteria

- Patients with at least one iv LCM administration (earliest administration defines index date)
- At least 1 encounter with iv LCM administered before 30 days of age.

### 5.2.4 Neonates exclusion criteria

- No exposure to either oral or iv LCM prior to the index date

### 5.2.5 Dosing criteria for groups

Once the LCM population is identified dose thresholds are applied to define the “Recommended Dose Group” and the “Loading Dose Group”). The following thresholds apply:

The recommended loading dose groups are as follows:

- $< 4$  mg/kg for patients less than 30 kg and less than 6 months of age
- $< 6$  mg/kg for patients less than 30 kg and greater than or equal to 6 months of age
- $< 4$  mg/kg for patients between 30 and 50 kg
- $< 200$  mg for patients
- greater than 50 kg

Note: Whilst babies are allowed higher mg/kg dosing than older children, due to issues of metabolism and weight, babies under 6 months of age have immature organs and a loading dose should be lower than older babies under 1 year.

High dose group have doses greater than the recommended group cut limits, applicable for age and weight.

- $\geq 4$  mg/kg for patients less than 30 kg and less than 6 months of age
- $\geq 6$  mg/kg for patients less than 30 kg and greater than or equal to 6 months of age
- $\geq 4$  mg/kg for patients between 30 and 50 kg
- $\geq 200$  mg for patients greater than 50 kg

## 5.3 Methodological techniques for patient selection

The selection criteria will be applied using the PEDSnet CDM data. First, the higher IV LCM cohort will be selected. Thereafter, the recommended initial/maintenance IV LCM cohort will be selected. The cohorts will be mutually exclusive, therefore a patient can only be included in one cohort. The medical chart review will only include eligible patients who fulfill the selection criteria and are identified using the PEDSnet CDM data.

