## 5.2 Study population

The study population will consist of the following two mutually exclusive cohorts:

- Pediatric patients treated with higher IV LCM doses (including UCB's defined loading dose), regardless of diagnostic code i.e. patients do not have to have a formal diagnosis of specific types of epilepsy and they may include children with SE caused by other conditions.
- Pediatric patients treated with recommended initial/maintenance IV LCM dose regardless of diagnostic code i.e. patients do not have to have a formal diagnosis of specific types of epilepsy and they may include children with SE caused by other conditions.

These two groups are defined by the proposed alternative higher initial dosage (first dose, first treatment in observed episode) and the recommended initial dosage (first dose, first treatment in observed episode) and patients remain in that group thereafter. Switching is not allowed at any time.

Patients will be initially identified using the following study criteria.

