### 5.2.1 Inclusion Criteria

- Patients with at least one iv LCM administration (earliest administration defines index date)
- At least 1 encounter with iv LCM administered between ages of  $\geq 1$  month and  $< 17$  years

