### 5.3.1 Patient selection period

The study period will be from the earliest data availability to the latest data availability based on the eligible patients identified. The PEDSnet CDM includes any person with at least one encounter with the member health system after December 31, 2008 which included a visit with a clinician; and one or more coded diagnoses were recorded in the person's record after December 31, 2008. For persons meeting these criteria, any available data is included in the PEDSnet CDM, including data earlier than 2009.

The study period will not be restricted by the FDA approval date for LCM, as it occurred in 2008 before the earliest date of data availability in the PEDSnet database.

The exposure to IV LCM will be defined by the presence of RxNorm codes for generic or brand name of IV formulations of LCM as indicated below in Section 5.5.4.

The index date for the higher IV LCM cohort will be the earliest of either of the following identified during the study period and with the required 3-month baseline period:

- a new treatment episode for an IV LCM dose (as described in Section 5.2 ); or
- receipt of a first higher IV LCM dose than known maintenance dose (as described in Section 5.2 .

The index date for the recommended initial dosage/maintenance IV LCM cohort will be the earliest of the following identified during the study period and with the required 3-month baseline period:

- a new treatment episode corresponding to an recommended initial dosage or a slow up-titration (as described in Section 5.2 )

IV LCM is usually administered in an inpatient setting for treatment of severe seizure conditions. We therefore anticipate the level of detail recorded for clinical information for the patients treated with IV LCM will be comprehensive as most of the patients will be treated in an inpatient setting.

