**Table 2 NDC codes for Lacosamide**

NDC	Description
00131181067	lacosamide 10 mg/ml injectable solution [Vimpat]
001311810	lacosamide 10mg/ml intravenous injection [Vimpat]
68842081067	lacosamide 10 mg/ml injectable solution [Vimpat]
00091181067	lacosamide 10 mg/ml injectable solution [Vimpat]

The treatment episode for IV LCM will be defined based on the prescription/dispensing information including dosage, formulation, date and time (as available in the database).

The IV LCM loading dose will be defined, where possible, as the single, initial high IV LCM dose which is followed within approximately 12 hours by a subsequent lower maintenance dose.

As we are evaluating IV LCM, which is usually administered in a hospital (inpatient) setting, it is anticipated that in most cases detailed dosage information will be recorded in the patients' medical chart with detailed information on individual IV LCM doses administered, including exact dosage data and time stamps indicating time of administration. This will enable the capture of IV LCM loading dose and the identification of subsequent episodes of IV LCM loading dose exposure.

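### The protocol has two conflicting rules for index date and dose group; if the Section 5.3.1 rule is followed, later dosing decides cohort membership and biases every rate ratio

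*Protocol*

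**What the plan says.** Two sets of current protocol text govern who enters which cohort and when follow-up starts.

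- **First-dose rule (Sections 5.2, 5.2.1, 5.2.5).** Inclusion reads "Patients with at least one iv LCM administration (earliest administration defines index date". Group is set by the first dose of the first treatment in the observed episode, compared with age- and weight-specific cut-offs, and "patients remain in that group thereafter. Switching is not allowed at any time".
- **Later-dose rule (executive summary, Sections 5.1 and 5.3.1).** For the higher cohort, the index date is the earlier of a new IV LCM episode or "receipt of a first higher IV LCM dose than known maintenance dose". The comparator has no such alternative; its index is a new episode at the recommended initial dose or on slow up-titration.
- **Selection order (Section 5.3).** "First, the higher IV LCM cohort will be selected. Thereafter, the recommended initial/maintenance IV LCM cohort will be selected", and each child may be in one cohort only.
- **Clean baseline.** The executive summary requires a baseline free of oral and IV LCM. Section 5.2.2 lists the same condition, but as an exclusion: "No exposure to either oral or iv LCM within the 3 months prior to the index date". Section 5.2.4 has the same reversal for neonates. Section 5.3.2 counts the 3 months back from the start of the qualifying episode.
- **Age.** Section 5.2.1 asks for "At least 1 encounter with iv LCM administered between ages of" 1 month and 17 years, without tying age to the index dose.
- **Loading-dose description (Section 5.5.4).** Where possible, a loading dose is "the single, initial high IV LCM dose which is followed within approximately 12 hours by a subsequent lower maintenance dose".

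**The concern.** A cohort comparison needs one time zero, with group membership settled by what is known at that time. The first-dose rule does this. The later-dose rule does not: a child who begins below the cut-off and is later given more than the maintenance dose can be classed as higher-dose because of something that happened after treatment began. As the higher cohort is drawn first and the cohorts are exclusive, that child also disappears from the comparator.

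To be given a later dose, a child must still be in hospital, and will often be a child who has tolerated the drug so far. Grouping on that information distorts the IRR even if dose has no effect. The propensity score in Section 5.9.1.1 uses baseline characteristics, so inverse-probability weighting cannot correct a group label that depends on the post-initiation course. The distortion would reach every primary and secondary IRR, and it would weaken the new-user design on which Section 5.9.4 relies.

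**Working it through.** **Step 1: set the rules side by side.**

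| Item | Sections 5.2, 5.2.1, 5.2.5 | Sections 5.1, 5.3, 5.3.1, executive summary |
|---|---|---|
| Index date | First IV LCM dose, both groups | Higher cohort: possibly a later dose. Comparator: new episode only |
| Group | First dose against fixed cut-offs | Higher cohort also through a dose above the child's own maintenance dose |
| Later doses | Change nothing | Can move a child into the higher cohort |
| Order of selection | Irrelevant, because the cut-offs do not overlap | Decisive, because the higher cohort is filled first |

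Section 5.3.1 refers to Section 5.2 for the later-dose route, but current 5.2 and 5.2.5 contain no such definition. Section 15 shows that the superseded 5.2 did. The amendment replaced 5.2 and left 5.1, 5.3.1 and the executive summary as they were.

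**Step 2: test the route against the clean baseline.** A known maintenance dose implies earlier LCM. If the 3 LCM-free months are counted back from the later dose, almost no child can qualify by this route. If they are counted back from episode start, as Section 5.3.2 allows, the route is open and time zero can fall after earlier LCM doses.

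**Step 3: illustrate the consequence.** The protocol has no power or effect-size figure to reproduce. Its 875 (Section 5.9.3) is a feasibility count, not split by dose group. A simulation with no true dose effect (2,000,000 children per scenario, 36 scenarios) compared three readings:

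- A: group and index at the first IV dose (Section 5.2).
- B: higher cohort if ever escalated, index at the first IV dose.
- C: higher cohort if ever escalated, index at the later dose.

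IRR = (first events / patient-days, higher cohort) ÷ (first events / patient-days, comparator).

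The assumed inputs, apart from the 37-day cap (Section 5.3.3), are not from the protocol:
- 30%, 50% or 70% start high, at random.
- 10%, 25% or 50% of low starters are planned to escalate on days 1 to 7, and do so only if still inpatient and event-free.
- Event hazard is 0.01 per day, with first-day hazard 1 or 10 times that. The tenfold case reflects the expectation in Section 5.9.4 that most events fall within 24 hours.
- Half the children have 1 or 3 times the event hazard; in the threefold case they are also likelier to escalate.
- Mean stay is about 10 days.

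| Start high | Planned escalation | First-day hazard | Severity | A | B | C | Moved, of 875 |
|---|---|---|---|---|---|---|---|
| 30% | 25% | 1x | 3x | 1.00 | 0.92 | 1.03 | 100 |
| 30% | 50% | 1x | 1x | 1.00 | 0.68 | 0.80 | 211 |
| 30% | 50% | 10x | 1x | 1.00 | 0.43 | 0.51 | 193 |
| 50% | 10% | 1x | 3x | 1.00 | 0.98 | 1.00 | 28 |
| 50% | 25% | 10x | 1x | 1.01 | 0.74 | 0.79 | 69 |
| 70% | 10% | 10x | 3x | 1.00 | 0.93 | 0.94 | 14 |

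Across all 36 scenarios, A runs from 0.99 to 1.01, B from 0.43 to 0.98 and C from 0.51 to 1.03. To two decimals, B is below 1 in all 36 and C in 32. In the 50%/25%/10x row, 15.8% of low starters move: 0.5 × 0.158 × 875 ≈ 69 children.

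The mechanism is simple. A moved child has, by construction, passed the days before escalation without an event. The comparator loses that event-free time but keeps the children with early events. Under B, the higher cohort also gains that time.

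**The case against.** The strongest reply is that Section 5.2 is the amended, specific text. It fixes group by first dose, forbids switching and uses disjoint cut-offs, so the order in Section 5.3 is merely a programming sequence. Section 5.3.1 also takes the earlier of its two events with a required clean baseline, and for an LCM-free child the new episode comes first or coincides. On that reading, the later-dose route is nearly empty. This stands as a limit: the harm arises only if 5.3.1 is followed and the baseline is anchored at episode start. It does not remove the contradiction, because the route remains in three places of current text and the protocol does not say which rule prevails.

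A reader might infer four stronger points that the document does not support.

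- **That the IRR is biased upward because sicker children escalate.** Such an example needs assumed risks and ignores patient-days and the need to remain in hospital until escalation. With those included, the ratios are mostly below 1, even when escalators carry threefold hazard.
- **That the comparator holds only children who never escalated.** Section 5.3.1 keeps slow up-titration there.
- **That the 12-hour description drops children whose LCM was stopped for a reaction.** It is qualified by where possible, Section 5.2.5 has no follow-on condition, and Section 5.3.3 provides follow-up for children with one IV dose and no further LCM.
- **That a child dosed as a neonate and again later is counted in both cohorts.** Section 5.3.3 includes each patient once. What remains is that age should be tied to the index dose.

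The reversed exclusion wording is a drafting slip, since the executive summary makes the intent plain. It should still be corrected, because read literally it keeps only prior LCM users.

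**Conclusion.** The concern holds in conditional form. Current text gives two incompatible rules for time zero and group, so cohort membership cannot be determined from the protocol alone. Under Section 5.2 there is no bias from this source. Under Section 5.3.1, with the baseline anchored at episode start, children are classified on post-initiation information and every IRR is affected.

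The direction and size are not known. The illustrative null IRRs of 0.43 to 1.03, with about 14 to 211 of 875 children moved, rest on assumed escalation, hazard and length of stay, and every scenario assumes that only event-free children escalate. They show that the error can be large and would usually make the higher dose look safer, which matters in a safety study. They do not estimate the bias in this one. No view is taken on which dose threshold is right.

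**What to change.** Replace the two rules with one, stated once and cross-referenced elsewhere:

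1. Time zero is the first recorded IV LCM dose, with age in range at that dose and no oral or IV LCM in the required baseline.
2. Group is that dose against the Section 5.2.5 cut-offs, unchanged by later doses.
3. Delete the index route based on a known maintenance dose from the executive summary and Sections 5.1 and 5.3.1, and the higher-cohort-first order from Section 5.3.
4. Reword Sections 5.2.2 and 5.2.4 so that any prior exposure in the stated window is the exclusion.
5. State in Section 5.5.4 that the 12-hour description does not determine group membership.

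The cost is protocol wording and simpler cohort code. No new data are needed.
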